9.0 Efficacy Analyses

9.1 General Considerations

Efficacy analyses for primary and secondary endpoints will be conducted in the ITT Population for the US and the mITT Population for the EU regulatory agencies. All other efficacy analyses will be conducted using the ITT population.

Analyses will be performed using a gated hierarchical testing procedure to preserve a family-wise Type I error rate of $\alpha = 0.05$.

To control the family-wise Type I error rate at 0.05 for multiplicity across the primary and secondary endpoints, a hierarchical testing strategy¹ will be used. For the US, the secondary endpoints assessed "over time" (see Section 3.2) will be excluded from the hierarchical testing strategy. [REDACTED]

[REDACTED] Nominal p-values will be provided thereafter.

The final analysis will be performed after all ongoing subjects have completed the study and the database has been locked. This will be the only analysis for the primary composite, coprimary and secondary efficacy endpoints, as well as all other efficacy endpoints.

Unless otherwise specified, categorical variables will be analyzed using Cochran-Mantel-Haenszel (CMH) test, [REDACTED]. Continuous variables will

be analyzed using analysis of covariance (ANCOVA) [REDACTED]
[REDACTED]

Unless otherwise specified, any subject who is randomized based on a wrong stratum will be analyzed according to the subject's actual stratum.

"Baseline" refers to the last non-missing observation before the first administration of study drug or randomization if no study drug is given. The change from baseline values will be computed as the post-baseline value minus the baseline value.

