3 OBJECTIVES AND ENDPOINTS

3.1 Objectives, Hypotheses, and Estimands

The study objective is to compare the safety and efficacy of BOTOX with placebo for the treatment of platysma prominence in adult subjects with moderate to severe platysma prominence at maximum contraction.

The clinical hypothesis is that BOTOX is a safe and effective treatment for the temporary improvement in the appearance associated with moderate to severe platysma prominence in adults.

Estimands: Primary Endpoints

The attributes of the estimands corresponding to the primary efficacy endpoints are summarized in [Table 1](#).

Table 1. Summary of the Estimand Attributes of the Primary Efficacy Endpoints

Attributes of the Estimand					
Estimand Label	Treatment	Variable (Endpoint)	Population	Handling of Intercurrent Events	Statistical Summary
Hypothetical estimand for primary endpoint	Single dose of BOTOX [REDACTED] or placebo	Composite achievement of a Grade 1 or 2 (Minimal or Mild) and at least a 2-grade improvement from baseline based on both investigator's assessment using the C-APPS and subject's self-assessment using the P-APPS at maximum contraction at Day 14	Intent-to-treat (ITT) (all randomized)	Subjects who discontinue study prior to Day 14 assessments or who do not have Day 14 C-APPS or P-APPS assessments will be included in the analysis as a hypothetical scenario in which the assessments were conducted as per protocol	Response rates and rate differences between BOTOX and placebo treatment groups; Cochran-Mantel-Haenszel (CMH) test [REDACTED]
Hypothetical estimand for coprimary endpoints	Single dose of BOTOX [REDACTED] or placebo	Achievement of at least a 2-grade improvement from baseline based on the following: 
• Investigator's assessment using C-APPS at maximum contraction at Day 14, and• Subject's self-assessment using P-APPS at maximum contraction at Day 14	Modified intent-to-treat (mITT) [REDACTED]	Subjects who discontinue study prior to Day 14 assessments or who do not have Day 14 C-APPS or P-APPS assessments will be included in the analysis as a hypothetical scenario in which the assessments were conducted as per protocol	Response rates and rate differences between BOTOX and placebo treatment groups; CMH test [REDACTED]

Estimands: Secondary Endpoints

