7.7 Overall Type I Error Control

Analyses will be conducted using a gated hierarchical testing procedure to preserve a familywise Type I error rate of $\alpha = 0.05$.

To control the family-wise Type I error rate at 0.05 for multiplicity across the primary and secondary analyses, a hierarchical testing strategy ²³ will be used.

Nominal p-values will then be provided.

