7.8 Sample Size Determination

Approximately 400 subjects will be randomized into the study in a 1:1 ratio yielding approximately 200 subjects in the BOTOX group and 200 subjects in the placebo group in the treatment period. [REDACTED]

[REDACTED]

[REDACTED]

For the US FDA primary analysis, an estimated sample size of 360 subjects will give a power of greater than 99% to detect a difference in responder rates between the BOTOX and placebo groups, assuming a 10% dropout rate by Day 14. [REDACTED]

[REDACTED]

[REDACTED]

The primary analysis for EU regulatory agencies only will be performed on the mITT population, [REDACTED]

[REDACTED]

a sample size of 180 will result in a power of greater than 99% to detect a difference between BOTOX and placebo in the proportion of subjects achieving at least a 2-grade improvement from baseline according to both investigator's assessment using C-APPS and subject's self-assessment using P-APPS at maximum contraction at Day 14. [REDACTED]

[REDACTED]

[REDACTED]

All calculations are based on a 2-sided Type I error rate of 0.05. The power calculation is based on a 2-sample test of independent proportions, as implemented in the commercial software nQuery version 7.0.

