2.3 Treatment Assignment and Blinding

Subjects will be randomized to BOTOX or placebo in a 1:1 ratio. Randomization will be stratified at each investigational site by baseline C-APPS on Day 1 [REDACTED]

[REDACTED] The same block will not be shared across sites or by baseline C-APPS.

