13.0 Overall Type-I Error Control

To control the family-wise Type I error rate at 0.05 for multiplicity across the primary and secondary analyses [REDACTED]

Thus, the hierarchical testing order follows for US FDA:

1. Primary composite: Achievement of Grade 1 or 2 (Minimal or Mild) and at least a 2-grade improvement from baseline based on both investigator's assessment using the C-APPS and subject's self-assessment using P-APPS at maximum contraction at Day 14
2. Secondary: Responses of *Satisfied* or *Very satisfied* on the ANLFQ: Satisfaction (Follow-up) Item 5 (effect of treatment) at Day 14
3. Secondary: Responses of *Not at all bothered* or *A little bothered* on the BAS-PP Item 2 (jawline) at Day 14
4. Secondary: Responses of *Not at all bothered* or *A little bothered* on the BAS-PP Item 1 (vertical neck bands) at Day 14

5. Secondary: Change from baseline on the ANLFQ: Impacts summary score at Day 14

The hierarchical testing order follows for EU regulatory agencies:

1. Coprimary: Achievement of at least a 2-grade improvement from baseline based on the following:
 - Investigator's assessment using C-APPS at maximum contraction at Day 14
 - Subject's self-assessment using P-APPS at maximum contraction at Day 14
2. Secondary: Achievement of a rating of Minimal or Mild according to subject's self-assessment using P-APPS at maximum contraction at Day 14
3. Secondary: Responses of *Satisfied* or *Very satisfied* on the ANLFQ: Satisfaction (Follow-up) Item 5 (effect of treatment) at Day 14
4. Secondary: Responses of *Not at all bothered* or *A little bothered* on the BAS-PP Item 2 (jawline) at Day 14
5. Secondary: Responses of *Not at all bothered* or *A little bothered* on the BAS-PP Item 1 (vertical neck bands) at Day 14
6. Secondary: Change from baseline on the ANLFQ: Impacts summary score at Day 14
7. Secondary: Change from baseline on the ANLFQ: Impacts summary score at Days 30, 60, and 90

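### All five US confirmatory steps are at Day 14 and the four US over-time endpoints are left outside the hierarchy; they could be added after step 5 at no cost to the existing steps

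*SAP*

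**What the plan says.** SAP 9.1 sets up a gated hierarchical procedure at a family-wise rate of 0.05 and then limits it: "For the US, the secondary endpoints assessed 'over time' (see Section 3.2) will be excluded from the hierarchical testing strategy". After a redaction, it says that nominal p-values follow the hierarchy.

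SAP 3.2 lists eight US secondary endpoints. Four are over-time endpoints: Grade 1 or 2 on C-APPS, Grade 1 or 2 on P-APPS, at least a 1-grade improvement on C-APPS, and the same on P-APPS. The visits they cover are redacted. SAP Table 2 assigns each of them a CMH test, so between-group testing is planned.

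SAP 13.0 gives the US order in full. Step 1 is the composite primary, and the last step is "5. Secondary: Change from baseline on the ANLFQ: Impacts summary score at Day 14". All five steps are at Day 14. The EU order in the same section ends with "7. Secondary: Change from baseline on the ANLFQ: Impacts summary score at Days 30, 60, and 90".

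The hypothesis in Protocol 3.1 reads in part: "The clinical hypothesis is that BOTOX is a safe and effective treatment for the temporary improvement in the appearance associated with moderate to severe platysma". Protocol 4.1 schedules visits after treatment at Days 14, 30, 60, 90 and 120.

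**The concern.** An effect described as temporary has a time course, and the trial records C-APPS and P-APPS response along it. The four excluded endpoints are the only visible US efficacy endpoints that can extend past Day 14. With them outside the hierarchy, a US statement about response at a later visit can rest only on p-values with no multiplicity control, however clear the data are.

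The Day 14 conclusions are not at stake. What is at stake is whether later-visit evidence that the trial already collects, and already plans to test, can have confirmatory standing in the US.

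**Working it through.** **Inputs.** Family-wise alpha is 0.05 (SAP 9.1: "Analyses will be performed using a gated hierarchical testing procedure to preserve a family-wise Type I error rate of" 0.05) and tests are two-sided (Protocol 7.8: "All calculations are based on a 2-sided Type I error rate of 0.05"). There are five US steps (SAP 13.0) and four over-time endpoints (SAP 3.2). The correlation between test statistics is not given, so 0 to 0.9 is assumed.

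**1. The plan's own figure.** In a fixed sequence each step is tested at 0.05 and testing stops at the first failure. A false claim requires rejecting the first true null in the order, so the family-wise error is at most 0.05 for any number of steps. Simulation (400,000 draws) with five steps, all null, gave 0.051 at correlation 0 and 0.050 at correlation 0.5. The stated 0.05 is reproduced for the listed steps.

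**2. Four tests appended as steps 6 to 9.** Whether steps 1 to 5 are rejected depends only on their own p-values.
- Decisions on steps 1 to 5 were identical in every simulated trial with and without the added steps.
- All nine null: 0.051 and 0.050 at correlations 0 and 0.5, the same as with five steps.
- Steps 1 to 5 strongly effective, steps 6 to 9 null: 0.050 at both correlations.

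The alpha and power of steps 1 to 5 are therefore unchanged.

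**3. The four endpoints left nominal.** Suppose there is no true effect at one late visit, with one two-sided 0.05 test per endpoint. Under independence, P(at least one false positive) = 1 − 0.95⁴ = 1 − 0.8145 = 0.185. With equal correlation ρ between statistics:

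| ρ | P(at least one of four) |
|---|---|
| 0 | 0.185 |
| 0.5 | 0.156 |
| 0.8 | 0.114 |
| 0.9 | 0.093 |

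Positive correlation is to be expected. The endpoints are two scales rated on the same subjects, and for a rating that starts at Grade 3, reaching Grade 1 or 2 and improving by at least one grade are the same event.

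**4. How the added steps must be built.** An over-time endpoint spans several visits. One step that counted success at any of four or five visits would have error 1 − 0.95⁴ = 0.185 or 1 − 0.95⁵ = 0.226 under independence (0.156 or 0.184 at correlation 0.5), which breaks the control. A step must be one test, or must require every component to reach p<0.05; in the second case its error is at most 0.05.

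**5. What the added steps can achieve.** They are reached only if steps 1 to 5 all succeed. The joint power of those steps is not visible. As an assumed illustration, 90% power at each gives 0.9⁵ = 0.59 if independent and about 0.71 at correlation 0.5 (simulated).

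**The case against.** The strongest reply is that this is a legitimate, prespecified choice. The exclusion is stated openly, the US order is enumerated exactly, and a sponsor may keep secondary endpoints outside the hierarchy. That stands: there is no error here and no contradiction between the US lists.

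Four stronger readings are tempting, and the documents do not support them.

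- *The plan fails its own error-control claim.* Protocol 7.7 says "To control the family-wise Type I error rate at 0.05 for multiplicity across the primary and secondary analyses, a hierarchical testing strategy" will be used, and half of the US secondary endpoints lie outside it. But SAP 9.1 narrows its claim in the very next sentence, and Protocol 7.7 and SAP 13.0 are partly redacted, so the same limit may stand there.
- *Subjects are followed to Day 120 in order to establish duration.* No passage says so. The hypothesis speaks of temporary improvement without stating a duration, and adverse events, a primary endpoint for both regions, are assessed through Day 120. No visible passage plans a confirmatory persistence claim.
- *The false-positive risk is above 50%.* Sixteen or 20 independent null tests give 0.56 or 0.64. Those counts assume which visits are tested, require no effect as early as Day 30 or even Day 14, and ignore correlation. In Phase 2, at least a 1-grade improvement at Day 14 was significant on both scales at p<0.0001 (Protocol 2.2).
- *The EU plan confirms what the US plan leaves out.* EU step 7 is a psychosocial questionnaire score. Neither visible order tests C-APPS or P-APPS response after Day 14. The EU order shows only that late visits can stand at the end of a sequence.

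What remains after these concessions is that excluding the endpoints gains nothing for steps 1 to 5, and no reason for it is visible.

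**Conclusion.** The point holds as an improvement to a disclosed design choice. On the visible text, no US efficacy result after Day 14 is under Type I error control, and placing the four endpoints after step 5 would allow formal later-visit conclusions with steps 1 to 5 untouched and the family-wise error still at 0.05.

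The size is moderate: about 9% to 16% for at least one false positive at one late visit with no remaining effect, and 18.5% as the upper bound for four tests. This rests on an assumed equal correlation of 0.5 to 0.9, one test per endpoint at that visit, no true effect there, and nominal results being read as findings. Because the tested visits are redacted, any larger count is an assumption. The validity of the Day 14 primary analysis and of steps 2 to 5 is not affected.

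**What to change.** Before unblinding:

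1. Delete the exclusion sentence in SAP 9.1.
2. In SAP 13.0, append the over-time endpoints to the US order after step 5 as a fixed sequence, using the visits already defined for them, earliest first.
3. Within each visit, test both endpoint types (Grade 1 or 2; at least a 1-grade improvement) before moving to the next visit. Running one type through to the last visit first would let a late failure block the other type at early visits.
4. Make each step a single test, or require both C-APPS and P-APPS to reach p<0.05. Do not count success at any one of several visits.
5. Stop at the first failure and give nominal p-values after that. State that these steps are reached only if steps 1 to 5 all succeed.
6. Check that Protocol 7.7 agrees with the revised order.

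If the sponsor keeps the exclusion, add to SAP 13.0 that error control covers only the listed endpoints and that US over-time results are descriptive.

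The cost is SAP wording. It needs no new subjects, visits, data or alpha. With no interim analysis (SAP 12.0) and a single final analysis after database lock (SAP 9.1), the change does not disturb any planned earlier look.

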9.2 Handling of Missing Data

Missing data will be imputed using the following methods for the efficacy analyses:

- Multiple Imputation: The Multiple Imputation approach will be used as a primary analysis for the primary endpoint, as well as for all secondary endpoints. For the primary endpoint (US: primary composite endpoint; EU: coprimary endpoints) and the primary and secondary measures through Day 120 [REDACTED]

- Non-responder Imputation (NRI): The NRI analysis will categorize any subject who does not have evaluation during a specific visit window as a non-responder for that visit. The NRI will be one of the sensitivity analysis approaches in the analyses of categorical variables for efficacy.
- As Observed (AO): The AO analysis will not impute values for missing evaluations, and thus a subject who does not have an evaluation on a scheduled visit will be excluded from the AO analysis for that visit. AO will include all values collected in the study and will be used for sensitivity analyses of efficacy endpoints.

9.3 Primary Efficacy Endpoints and Analyses

9.3.1 Primary Efficacy Endpoints

Clinician Allergan Platysma Prominence Scale (C-APPS): The sponsor developed the C-APPS as a clinician's assessment tool for evaluation of platysma prominence at maximum contraction. [REDACTED]

[REDACTED]

[REDACTED]

[REDACTED]

[REDACTED]

Prior to enrolling subjects, investigators (or sub-investigators when applicable) will be trained in grading platysma prominence severity using the C-APPS.

The C-APPS is to be performed by the same trained and qualified (MD/DO) evaluator throughout the study [REDACTED]

[REDACTED]

[REDACTED]

[REDACTED]

Platysma prominence [REDACTED] will be assessed live, independently, at maximum contraction by the investigator using the C-APPS (1 = Minimal, 2 = Mild, 3 = Moderate, 4 = Severe, 5 = Extreme).

There are no COVID-19 protocol modifications for the C-APPS procedure. If a site visit is missed at which this assessment was planned, the assessment will be skipped for that timepoint.

Participant Allergan Platysma Prominence Scale (P-APPS): The P-APPS has been developed as a subject self-assessment tool for evaluation of platysma prominence at maximum contraction [REDACTED] [REDACTED]

[REDACTED]

Subjects will use the P-APPS (1 = Minimal, 2 = Mild, 3 = Moderate, 4 = Severe, 5 = Extreme) [REDACTED] to self-assess the severity of their left and right platysma prominence at maximum contraction (left and right ratings captured separately).

There are no COVID-19 protocol modifications for the P-APPS procedure. If a site visit is missed at which this assessment was planned, the assessment will be skipped for that timepoint.

[REDACTED]

[REDACTED]

9.3.2 Main Analysis of Primary Efficacy Endpoints

The attributes of the estimands corresponding to the primary composite and coprimary efficacy endpoints for the US and EU regulatory agencies, respectively, are summarized in Table 1 (see Section 2.1).

Analysis of the primary endpoint will be conducted on the ITT population based on treatment as randomized for the US FDA analyses and on the mITT population based on treatment as randomized for the EU regulatory agencies.

US FDA: The primary responder composite endpoint for an achievement of Grade 1 or 2 (Minimal or Mild) and at least a 2-grade improvement in both C-APPS and P-APPS will be analyzed using the CMH method [REDACTED]

EU regulatory agencies: The coprimary responder endpoints for at least a 2-grade improvement in the C-APPS and P-APPS will be analyzed separately using the CMH method [REDACTED]

The evaluation of the equality of the proportions of responders for the primary endpoint at Day 14 will be based on the CMH test [REDACTED]

The 95% CI for the treatment

responder rate differences will be constructed using the normal approximation to the binomial distribution.

9.3.3 Sensitivity and Supplementary Analyses of the Primary Efficacy Endpoints

Sensitivity analyses of the primary efficacy variables will be performed to establish their consistency and robustness as well as to further characterize the extent of subjects' responses. As-observed data analysis, as well as missing as non-responder (using NRI) analysis [REDACTED]

9.4 Secondary Efficacy Endpoints and Analyses

[figure not shown]
9.4.1 Secondary Efficacy Endpoints

Bother Assessment Scale - Platysma Prominence (BAS-PP): BAS-PP is a 2-item PRO measure that asks subjects to rate how bothered they are by the appearance of their vertical neck bands (Item 1) and jawline (Item 2) [REDACTED]

Appearance of Neck and Lower Face Questionnaire (ANLFQ): ANLFQ-Impacts is a 7-item PRO measure that assesses the psychosocial impact of the appearance of the neck and lower face from the subject perspective. [REDACTED]

[REDACTED] Scores from the individual items are summed [REDACTED] where higher scores indicate greater negative impact from the appearance of the neck and lower face.

ANLFQ-Satisfaction is a PRO measure that assesses treatment expectations and satisfaction with platysma prominence from the subject perspective. [REDACTED]

9.4.2 Main Analyses of Secondary Efficacy Endpoints

The attributes of the estimands corresponding to the secondary efficacy endpoints are summarized in Table 2 (see Section 2.1).

Analysis of the secondary endpoints will be conducted on the ITT population based on treatment as randomized for the US FDA analyses and on the mITT population based on treatment as randomized for the EU regulatory agencies.

For the secondary endpoints, the proportion of responders will be analyzed using the CMH test

9.4.3 Sensitivity and Supplementary Analyses for Secondary Efficacy Endpoints

Additional sensitivity analyses may be performed as needed to assess impact of missing data for secondary endpoints due to a pandemic or natural disaster.

9.4.4 Supportive Secondary Efficacy Endpoints and Analyses

Not applicable.

9.5 Additional Efficacy Analyses

For more information, contact the Office of the Vice President for Research and Economic Development at [contact] or [contact].

9.6 Efficacy Subgroup Analyses

Efficacy analyses for the primary composite and coprimary endpoints will be performed by subgroups of sex, age group [REDACTED], BMI [REDACTED] race [REDACTED] ethnicity [REDACTED] region [REDACTED] and baseline C-APPS at maximum contraction [REDACTED]

10.0 Safety Analyses

10.1 General Considerations

Safety data will be summarized for the Safety Analysis Set. Safety summaries will be presented by treatment group. For the safety analysis, subjects are assigned to a treatment group based on the treatment actually received, regardless of the treatment randomized.

The safety parameters will include incidence of AEs and change from baseline in vital signs. For each safety parameter evaluating change from baseline, the last nonmissing safety assessment before study drug administration will be used as the baseline for all analyses of that parameter.

10.2 Adverse Events

Adverse events (AEs) will be summarized and presented using primary MedDRA System Organ Classes (SOCs) and preferred terms (PTs) according to the version of the MedDRA coding dictionary used for the study at the time of database lock. The actual version of the MedDRA coding dictionary used will be noted in the AE tables and in the clinical study report. Specific adverse events will be counted once for each subject for calculating percentages, unless stated otherwise. In addition, if the same adverse event occurs multiple times within a subject, the highest severity and level of relationship to investigational product will be reported.

